Official title

Comparative study of the effect of continuous caudal epidural with general anaesthesia versus general anaesthesia on intra operative and post operative analgesic requirements for lumbar fixation

DOCUMENT DATE:
APRIL 9, 2025

protocol

Comparative study of the effect of continuous caudal epidural with general anaesthesia versus general anaesthesia on intra operative and post operative analgesic requirements for lumbar fixation

Thesis

Submitted for Partial Fulfillment of M.D. Degree
in **Anaesthesiology, Intensive Care and Pain Management**

By

Postgraduate Student: [name]
Degree: M.B.B.CH., M.Sc., (Ain-Shams University)

Under Supervision of

DIRECTOR: [name] [name]

Academic Position: Professor of Anaesthesia, Intensive Care and Pain Management, Faculty of Medicine, Ain Shams University

CO-DIRECTOR: [name] [name]

Academic Position: Professor of Anaesthesia, Intensive Care and Pain Management, Faculty of Medicine, Ain Shams University

CO-DIRECTOR: [name] [name]

Academic Position: Lecturer of Anaesthesia, Intensive Care and Pain Management, Faculty of Medicine, Ain Shams University

CO-DIRECTOR: [name] [name]

Academic Position: Lecturer of Anaesthesia, Intensive Care and Pain Management, Faculty of Medicine, Ain Shams University

What is already known on this subject? AND What does this study add?

Caudal epidural anaesthesia has been used successfully in adult patients either as primarily sole anaesthetic technique or adjuncts to general anaesthesia to provide post operative analgesia. Pre-emptive caudal epidural is a proven technique for providing analgesia for spinal surgeries. Challenging aspect of spine surgery is to provide extended post operative analgesia.

This study is designed to evaluate the effectiveness of continuous caudal epidural for intra operative analgesia as alternative to opioid analgesia in general anaesthesia and reducing post operative opioid requirements to control post operative pain.

1. INTRODUCTION/ REVIEW

Pain control during intra operative and post operative period for spine surgeries is crucial in patients as poor pain control may result in morbidity and mortality (**Fawzi & Almarakbi, 2012**). Severe acute pain prolongs hospital stay, delays mobilization and promotes subsequent chronic post-surgical pain (**Schug & Bruce, 2017**).

Whilst general anaesthesia is commonly used to undertake spine surgery, the use of neuraxial and peripheral regional anaesthesia techniques for intra operative and post operative analgesia is an evolving practice (**Gerbershagen et al., 2013**). Multimodal analgesia, including opioids, is used to limit pain after spinal surgery. Common adverse effects of opioids include nausea, constipation, ileus, delirium, itching, respiratory depression and respiratory tract infection (**Eochagain et al., 2022**).

Caudal anaesthesia was described in 1901 by two French physicians, Fernand Cathelin and Jean-Anthanase Sicard (**Waurick & Waurick, 2015**). The caudal epidural block was first introduced as a landmark-based, blind technique. Success rate in adults was 68–75% even in the experienced hands. Because of the inaccuracy of blind technique, some authors have recommended that caudal epidural injection is performed under fluoroscopic guidance (**Barham & Hilton, 2010**). Continuous caudal analgesia was first applied clinically, in 1941, being used to relieve pain for an

operation upon the lower extremity (**Kao & Lin, 2017**). Caudal epidural anaesthesia/analgesia is the most widely employed technique for various surgical procedures within the distribution of T10–S5 dermatome and it is easier to perform caudal procedure in the prone position (**Hurley, 2010**).

Caudal analgesia is a good, reliable and easy method to provide intra operative and post operative analgesia. However, the single shot caudal analgesia is short in duration, so the catheter injection may be used to prolong the analgesia time as continuous caudal epidural (**El-Feky & Abd El Aziz, 2015**).

Caudal epidural analgesia, as pre-emptive analgesia, is an underutilized technique in adult patients undergoing lumbosacral spine surgeries. Caudal epidural block before surgery acts by blocking sensory input at the spinal cord level. Thus, pre-emptive analgesia has an important role in providing effective pain relief after lumbosacral spine surgeries (**Al Oweidi et al., 2010**). The combined caudal epidural analgesia with general anaesthesia is a proven technique in providing analgesia and managing post operative pain in lumbar spine procedures (**Lakshminarasimhaiah G et al., 2018**). It provides prolonged pain relief with adequate sensory block and limited motor blockade for early mobilization (**Nagappa et al., 2018**).

Among all available local anaesthetic bupivacaine is most commonly used. It produces a denser sensory block and enables better control of sensory and motor blockade while having the least incidence of an incomplete block (**Benyahia et al., 2015**).

Common complications associated with caudal anaesthesia include: Subdural, intravascular, or intraosseous injection, infection, hypotension, nerve roots injury, rectum perforation, hematoma formation, local anaesthetic toxicity, delayed respiratory depression, urinary retention, sacral osteomyelitis (**Wiegele et al., 2019**). A devastating complication of a caudal block is total spinal anaesthesia that can occur from an inadvertent dural puncture with subsequent intrathecal injection of local anaesthetic. Also, caudal epidural blocks have a higher incidence of local anaesthetic-related seizures (**Schug & Bruce, 2017**).

The overall benefit of intravenous analgesia versus caudal analgesia is still controversial, although many studies have shown that caudal epidural analgesia provides superior post operative analgesia compared to intravenous analgesia (**Kumar et al., 2017**).

In this clinical study, we will justify the current practice of combined continuous caudal epidural with general anaesthesia in adult patients undergoing lumbar fixation versus general anaesthesia. Furthermore, we will determine the analgesic

requirement, rescue analgesia, hemodynamic changes and possible complications with continuous caudal epidural analgesia.

2. AIM/ OBJECTIVES

The aim of this study is to evaluate the effectiveness of combined continuous caudal epidural with general anaesthesia versus general anaesthesia for intra operative and post operative analgesia in patients undergoing lumbar fixation, by recording intra operative and post operative analgesic requirements, blood pressure and heart rate and post operative patient-reported pain on the numeric pain scale score.

3. METHODOLOGY:

Patients and Methods

- **Type of the study:** Interventional, prospective, comparative randomized clinical trial.
- **Study Setting:** The operating theaters of Ain Shams University Hospitals.
- **Study period:** Over six months, after the approval of Medical Research Ethical Committee.
- **Study population:**

Inclusion criteria:

- Age group: Adult patients from age of 21 years to 60 years
- Sex: Both sexes.
- ASA Classification: patients with ASA classification I, II.
- Elective lumbar fixation surgeries.

Exclusion criteria:

- Patients refuse to give informed consent.
- Patients younger than 21 or older than 60.
- History of bupivacaine allergy.
- Emergency surgeries.
- Patients who underwent previous spine surgeries of any cause.

- Infection at the site of injection.
- Coagulopathy (acquired, induced, genetic).
- ASA Classification: ASA III, IV.
- Severe aortic stenosis, severe mitral stenosis, hypertrophic obstructive cardiomyopathy.
- Severe hypovolemia, Severe uncorrected anemia.
- Increased intra-cranial pressure (i.e., brain tumor or recent head injury).

Sampling method:

Patients will be randomly allocated by computer generated randomization into two equal groups A and B.

- **Group A:** Patients doing lumbar fixation with combined continuous caudal epidural and general anaesthesia.
- **Group B:** Patients doing lumbar fixation under general anaesthesia (opioid analgesia).

Sample size justification:

Using PASS 15 program for sample size calculation and according to (**Abdelhady et al., 2022**), the expected mean intra-operative narcotic consumption among study groups is $186.5 \pm 21.6 \mu\text{g}$ and $106 \pm 16.4 \mu\text{g}$.

Sample size of 30 patients per group can detect the difference between two groups with power $>90\%$ and alpha error 0.05.

Ethical considerations:

The study protocol will receive ethical approval from the Medical Research Ethical Committee, Faculty of Medicine, Ain Shams University. Informed written consent will be obtained from each patient before patients' allocation.

Study Procedures:

Patients will be randomly allocated into two equal groups.

Preoperative setting:

- Pre-operative assessment will be done by accurate history taking, full physical examination, laboratory and radiological investigations. including complete blood count (CBC), liver function test (LFT), kidney function test (KFT), prothrombin time (PT) and partial thromboplastin time (PTT) will be checked.
- All patient will be fasting for 8 hours pre operative.
- All patients will be informed about the study design, objectives and techniques.

- Informed consent will be signed by every patient prior to inclusion in the study.
- All patients will be educated about numeric pain scale score which 0 means no pain and 10 means worst imaginable pain.

Intraoperative setting:

- Standard perioperative monitoring will include pulse oximetry, electrocardiogram, end-tidal CO₂ measurement, inhaled volatile agent concentration and non-invasive blood pressure measurement.
- Baseline parameters such as oxygen saturation, systolic, diastolic and mean blood pressure, heart rate will be observed.
- Intravenous line will be inserted.
- For all patients, general anaesthesia will be induced by intravenous route using midazolam 0.04 mg/kg, fentanyl 1 µg/kg, propofol 2 mg/kg, atracurium 0.5 mg/kg.
- This will be followed by endotracheal intubation and mechanical ventilation. Maintenance of anaesthesia will be achieved by isoflurane 1.5% in oxygen and air (50:50) and atracurium 0.1 mg/kg every 20 minutes, so as to maintain end tidal CO₂ between 35 to 40 mm Hg.
- Intra operative heart rate and mean blood pressure will be recorded. Estimated blood loss will be determined.

Group A: (continuous caudal epidural with general anaesthesia “study group”)

- After induction of anaesthesia as mentioned above, patients will be located in the prone position for caudal epidural block. Sterile skin preparation and draping of the entire region will be completed in the standard fashion.
- Fluoroscopy will be utilized and a lateral view will be obtained to demonstrate the anatomic boundaries of the sacral canal. With fluoroscopy, the caudal canal will appear as a translucent layer posterior to the sacral segments. The median sacral crest will be visualized as an opaque line posterior to the caudal canal. The sacral hiatus will be visualized as a translucent opening at the base of the caudal canal. The coccyx will be seen articulating with the inferior surface of the sacrum. A 17- or 18-gauge Tuohy-type needle will be inserted in the midline into the caudal canal. A feeling of a slight “snap” may be appreciated when the advancing needle pierces the sacrococcygeal ligament. Once the needle reaches the ventral wall of the sacral canal, it will be withdrawn and reoriented, directing it more cranially (by depressing the hub and advancing) for further insertion into the canal. The anteroposterior view will be used once the epidural needle is safely situated within the canal and the

epidural catheter will be advanced cephalad. In this projection, the intermediate sacral crests will appear as opaque vertical lines on either side of the midline. The sacral foramina will be visualized as translucent and nearly circular areas lateral to the intermediate sacral crests. Once the correct placement of the needle will be confirmed, a catheter will be inserted into the desired location while depth and position will be confirmed fluoroscopically.

- Before the local anaesthetic will be injected, careful aspiration or passive drainage is essential to exclude an unintentional intravascular or intrathecal needle location. An initial dose of 20 ml of 0.25% bupivacaine will be injected in the caudal canal in order to perform sensory block and spare motor power. Then a dose of 10 ml 0.25% bupivacaine will be injected through the epidural catheter every 1-hour intra operatively and at 0-hour and 1-hour post operative. Then the catheter will be removed 1 hour post operative.

Group B: (general anaesthesia “control group”)

- General anaesthesia will be induced as described above with administration of extra doses of fentanyl as needed according to hemodynamic changes suggesting pain sensation.

Post-operative setting:

- After completion of surgery, the residual neuromuscular block will be reversed with injection of neostigmine 0.05 mg/kg and atropine 0.01 mg/kg. When patients become suitable for extubation, with stable hemodynamic and adequate muscle power, thorough oral and endotracheal suction followed by extubation will be done.
- Patients will be nursed in post anaesthesia care unit for monitoring of post operative vital signs and for post operative pain assessment by numeric pain scale score at 0-hour and management accordingly.
- Patients postoperative pain will be followed up at the ward at time interval 0, 1, 2, 4, 6 hours.
- Patients will undergo close monitoring for the first 6 hours after caudal injection for overdose or adverse reactions.
- The following factors will be assessed:
 - (1) Intra operative heart rate and blood pressure.
 - (2) Post operative pain assessment according to numeric pain scale score 1-10 as (0= no pain, 10 =worst imaginable pain) and hemodynamic parameters at 0, 1, 2, 4, 6 hours.
 - (3) Time to rescue analgesia (intravenous analgesia administered after

surgery) when the numeric pain scale score is 3 or higher. Patients with numeric pain scale score ≥ 3 at any point of time, will receive intravenous morphine 5mg.

- (4) Estimated blood loss and surgeon satisfaction of surgical field.
- (5) Total intra operative and post operative analgesia in both groups.
- (6) Common complications of caudal block in the postoperative period which include hypotension, bradycardia, lower limb numbness and urinary retention. These complications will be recorded and managed accordingly.

Measured outcomes:

Primary outcome:

- Determining the total amount of fentanyl that will be consumed as intra operative analgesia.

Secondary outcome:

- Determining the total amount of morphine that will be given as analgesia for the first 6 hours post operative.
- Analyzing the numeric pain scale score for the first 6 hours post operative.
- Detecting effect of continuous caudal epidural analgesia on intra operative and post operative hemodynamic changes.
- Identifying the time to the first demand for rescue analgesia.
- Justifying the use of continuous caudal epidural for analgesia in lumbar fixation surgeries.

Statistical analysis:

- Statistical analysis will be carried out using the statistical software SPSS program. Description of quantitative data as mean and standard deviation and qualitative data as number and percentage.
- Comparison between the two groups will be done by using the Chi-square test, independent t-test or Mann-Whitney U-test according to the distribution of data. A p-value less than 0.05 will be considered statistically significant.

End point:

- Severe hemodynamic instability due to any surgical complication.
- Any surgical emergency that will need to reopen the patient in operating room.

- 6 hours post operative.

REFERENCES

- **Abdel Hady Sarah Mahmoud Farid Mahmoud, Ahmed Azza Youssef Ibrahim, Neamat-Allah Hatem Saaed Abdel Hamid, et al. (2022):** Combined caudal epidural with general anesthesia for lumbar discectomy. Ain Shams medical journal. 73(3): 695-704.
- **Benyahia Najoua Mokraï, Verster Ann, Saldien Vera, et al. (2015):** Regional anaesthesia and postoperative analgesia techniques for spine surgery – a review. Romanian Journal of Anaesthesia and Intensive Care. 22(1): 25-33.
- **El-Feky EM and Abd El Aziz AA. (2015):** Fentanyl, dexmedetomidine, dexamethasone as adjuvant to local anesthetics in caudal analgesia in pediatrics. Egypt J Anaesth. 31:175-80.
- **Eochagain Aisling Ni', Singleton Barry N., Moorthy Aneurin, Buggy Donal J. (2022):** Regional and neuraxial anaesthesia techniques for spinal surgery: a scoping review. British Journal of Anaesthesia. 129 (4): 598-611.

- **Hurley WR. (2010):** Acute postoperative pain. In: Miller RD, Eriksson LI, Fleisher LA, Wiener-Kronish JP, Young WL, editors. *Miller's Anesthesia*. 7th ed. Philadelphia: Churchill Livingstone. 2757-81.
- **Kao Sheng-Chin, Lin Chia-Shiang (2017):** Caudal Epidural Block: An Updated Review of Anatomy and Techniques. *BioMed Research International* 1:1-5.

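### The planned number of fixation levels is known before allocation and plausibly drives the fentanyl total, but neither the randomisation nor the stated comparison uses it: a loss of precision and face balance, not bias

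*Protocol*

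**What the plan says.** All references are to the Protocol, section 3 (Methodology), unless stated.

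- **Eligibility.** The inclusion criterion for surgery is "Elective lumbar fixation surgeries". The one exclusion on surgical history, "Patients who underwent previous spine surgeries of any cause", removes revisions but does not limit the number of levels.
- **Allocation (Sampling method).** "Patients will be randomly allocated by computer generated randomization into two equal groups A and B". No stratification factor is named, here or under Study Procedures.
- **Primary outcome (Measured outcomes).** "Determining the total amount of fentanyl that will be consumed as intra operative analgesia". It is not scaled to weight, duration or levels.
- **Dosing of the outcome drug.** Both groups receive the same weight-based fentanyl dose at induction. The Group B text adds "extra doses of fentanyl as needed according to hemodynamic changes suggesting pain sensation". The Group A text mentions no further fentanyl; it says that "10 ml 0.25% bupivacaine will be injected through the epidural catheter every 1-hour intra operatively".
- **Analysis (Statistical analysis).** Chi-square, independent t or Mann-Whitney tests, with no covariate. Neither levels nor operating time is in the list of factors to be assessed.
- **Planning figures (Sample size justification).** The text says "the expected mean intra-operative narcotic consumption among study groups is" 186.5 ± 21.6 µg and 106 ± 16.4 µg. The cited source appears in the References as "Combined caudal epidural with general anesthesia for lumbar discectomy".

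**The concern.** A total that is dosed as needed has more time and more stimulus to accumulate in a longer, more extensive operation. With 30 patients per group and no restriction by extent, the arms can differ by chance in their share of extensive cases. Ignoring extent also leaves its variation in the error term. Blood loss, pain scores and 6-hour morphine could be affected in the same way.

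The planned number of levels suits this purpose because it is fixed before allocation. Operating time is a poorer choice: it is measured after randomisation, and the block itself may change it. If planned levels are never recorded, later adjustment is impossible.

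The planning means and SDs come from a different operation, and the sample-size paragraph presents them as expected here without saying so. Nothing in the protocol shows what spread to expect in fixation.

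**Working it through.** **1. The plan's own power figure.** Inputs from Sample size justification; a two-sided test is assumed because sidedness is not stated.
- Difference = 186.5 − 106 = 80.5 µg.
- Pooled SD = √[(21.6² + 16.4²)/2] = 19.18 µg.
- Standardised difference = 80.5/19.18 = 4.20.
- Power with 30 per group (noncentral t) is practically 100%, so the statement of more than 90% is true.
- With 30 per group, 90% power needs a standardised difference of 0.851. The largest common SD that keeps 90% power is therefore 80.5/0.851 ≈ 94.6 µg, about 4.9 times the planned SD.

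**2. Chance imbalance.** Assumption: 30% of cases are long; the documents give no case mix.
- With two independent binomials (n = 30, p = 0.3), the arms differ by at least 5 long cases with probability 0.204 and by at least 6 with probability 0.120.
- If exactly 18 of the 60 cases are long, a gap of 6 or more has probability 0.158.
- Assume further that a long case adds D = 50 to 150 µg in both arms. A gap of 5 then moves the unadjusted difference by 5/30 × D = 8 to 25 µg, and a gap of 6 by 6/30 × D = 10 to 30 µg, against a planned 80.5 µg.

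**3. Gain from adjustment if levels act in both arms.** Assumption: levels explain R² = 20–50% of the variance. The standard error is multiplied by √(1 − R²).

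| R² | √(1 − R²) | Fall in SE | Equivalent extra patients, 1/(1 − R²) − 1 |
|---|---|---|---|
| 0.20 | 0.894 | 11% | 25% |
| 0.50 | 0.707 | 29% | 100% |

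**4. Gain from adjustment if levels act in Group B only.** This matches the text more closely, since as-needed fentanyl is written for Group B alone. Take the planning SDs as the spread at a given extent (assumption), p = 0.3, p(1 − p) = 0.21, and one common slope for levels, which settles near D/2.
- Unadjusted variance = [16.4² + 21.6² + 0.21 D²]/30.
- Adjusted variance ≈ [16.4² + 21.6² + 0.21 D²/2]/30.
- The two squared SDs sum to 735.52.
- D = 50: SE goes from √(1260.52/30) = 6.48 to √(998.02/30) = 5.77 µg, a fall of 11%.
- D = 150: SE goes from √(5460.52/30) = 13.49 to √(3098.02/30) = 10.16 µg, a fall of 25%.
- These are large-sample values. Simulation with 30 per arm, which includes the cost of estimating the slope, gives falls of about 9% and 22%.

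**5. What stratification adds on top.** With levels in the model and 30% long cases, leaving the randomisation unstratified inflates the variance by about 1.8%. Since √1.018 = 1.009, that is about 0.9% of the standard error. Nearly all the precision gain comes from adjustment; stratification mainly secures balance.

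**The case against.** The strongest case against is that broad eligibility with simple randomisation is a legitimate design for a 60-patient, single-centre trial, and that no stated figure fails. Adjustment may also sit in a statistical analysis plan that is not shown. Surgery is already limited to elective lumbar procedures at ages 21–60, ASA I–II, with no revisions. Much of this stands. It makes the point a cheap improvement, not a correction of an error. Stratification, however, belongs to the randomisation that this protocol describes, and so does recording levels before allocation.

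It can also be objected that extent is tied to fentanyl in one arm only. That is fair as a reading of the text, but step 4 shows that a useful gain remains.

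A reader might infer four stronger things, none of which the documents support:

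- **That chance imbalance cannot be told apart from the block's effect.** Randomisation balances extent in expectation, and the planned test's standard error already allows for chance imbalance. The test is valid without stratification.
- **That the spread in fixation is shown to exceed the planned spread.** No document gives an SD for fixation, and the source is known here only by its title.
- **That the trial is underpowered.** This needs a smaller effect as well as a larger SD. For example, with half the planned difference (40.25 µg) and an SD of 77.4 µg, power would be 51%. Both values are assumed, and the protocol supports neither.
- **That stratification itself yields the 11–29%.** That gain comes from adjustment, under an assumed R² and a linear model. It does not carry over directly if the Mann-Whitney test is used.

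**Conclusion.** The point holds as a missed gain in precision and balance. The protocol admits any elective lumbar fixation, measures an unscaled total that is dosed as needed in at least one arm, and leaves unused a baseline variable that plausibly drives it. There is no bias, the planned test is valid, and the power claim survives unless the SD is nearly five times the planned one.

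The size depends on inputs that the documents do not give: the share of long cases (30% assumed), the extra fentanyl in long cases (50–150 µg assumed) or the variance explained (20–50% assumed), and whether extent acts in one arm or both. Over these ranges the standard error falls by about 9–22% (Group B only) or 11–29% (both arms). If levels explain little of the variance, the gain is correspondingly small.

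On the planning figures, the supportable statement is narrow: they come from a discectomy study, and the spread in fixation is unknown.

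**What to change.** 1. Record the planned number of fixation levels before allocation.
2. Stratify the computer-generated randomisation by it in two strata, with the cut chosen by the sponsor from its own case mix. Use blocked lists within each stratum, because unrestricted lists would not produce balance.
3. Include planned levels as a covariate in the comparisons of total fentanyl and 6-hour morphine, or as a stratum if a rank test is used. This step brings most of the gain.
4. In Sample size justification, say that the planning figures come from a lumbar discectomy study and that the spread in lumbar fixation is unknown.

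If recruitment has begun, leave the randomisation as it is, record planned levels and adjust only.

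The cost is two lists instead of one, one field to complete before allocation and one term in the analysis. Group sizes may depart slightly from exactly 30 each if a block is left incomplete. No extra patients are needed, and eligibility stays as broad as now.

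### After a common induction dose, further fentanyl is written for Group B only, with no threshold or dose, yet total intra-operative fentanyl is the primary outcome

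*Protocol*

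**What the plan says.** All references are to the Protocol.

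- **Measured outcomes, primary:** "Determining the total amount of fentanyl that will be consumed as intra operative analgesia".
- **Intraoperative setting, common to both groups:** "For all patients, general anaesthesia will be induced by intravenous route using midazolam 0.04 mg/kg, fentanyl" at 1 µg/kg, with propofol and atracurium. Isoflurane 1.5% and scheduled atracurium follow for everyone.
- **Group B:** anaesthesia as above, with "administration of extra doses of fentanyl as needed according to hemodynamic changes suggesting pain sensation".
- **Group A:** an initial 20 ml of 0.25% bupivacaine, after which 10 ml of 0.25% "bupivacaine will be injected through the epidural catheter every 1-hour intra operatively and at 0-hour and 1-hour post operative". The paragraph does not mention fentanyl.
- **Factors assessed, item 5:** "Total intra operative and post operative analgesia in both groups".
- **Introduction:** the study will determine the analgesic "requirement, rescue analgesia, hemodynamic changes and possible complications with continuous caudal epidural analgesia".
- **Factors assessed, item 3:** a pain score of 3 or higher triggers morphine 5 mg after surgery. This rule is not limited to either group.

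**The concern.** Background anaesthesia is set the same for both arms. The drug decision left both arm-specific and discretionary is the one that generates the primary outcome. The text allows two readings.

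- **Literal:** Group A receives induction fentanyl only. The primary comparison then cannot separate an opioid-sparing block from a rule that lets only one arm be topped up.
- **Discretionary:** Group A may also be topped up, on the anaesthetist's judgement. No threshold is stated, no blinding is described, and only Group A has a catheter and hourly injections. Group A could be given less fentanyl for reasons other than better analgesia.

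Either way, a reader of the result would not know which rule produced it. A dosing rule is a trial procedure, so a statistical analysis plan could not supply it afterwards.

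**Working it through.** **1. The plan's own figure.** Sample size justification says "the expected mean intra-operative narcotic consumption among study groups is" 186.5 ± 21.6 µg and 106 ± 16.4 µg, with 30 per group, alpha 0.05 (two-sided assumed) and power above 90%.

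- Difference: 186.5 − 106 = 80.5 µg.
- Pooled SD: √((21.6² + 16.4²)/2) = √367.76 = 19.18 µg.
- Standardised difference: 80.5/19.18 = 4.20.
- Power at 30 per group is above 99.99%, so the stated claim holds.
- Smallest difference detectable at 90% power: 0.851 × 19.18 = 16.3 µg.

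The trial can therefore declare significance on differences far smaller than the one planned for.

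**2. What each reading implies.** Write a patient's total as 1 µg/kg × weight + top-up. Randomisation balances weight on average, so the expected difference (B − A) is B's mean top-up minus A's mean top-up. Under the literal reading A's term is zero, and the difference equals B's mean top-up whatever the block does. With one top-up of fixed dose it is

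dose × B's share topped up × (1 − ratio of A's share to B's).

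**3. Size if the block has no effect.** The Protocol supplies 30 per arm and 1 µg/kg. The following are assumptions: weight normal with mean 70, 80 or 90 kg and SD 12 or 15 kg (clipped to 40–140 kg); one 50 µg top-up; Group B share 10, 25, 50 or 75%; A:B ratio 0, 0.5, 0.8 or 1. Each setting used 10,000 simulated trials at two-sided alpha 0.05. Ranges are over the six weight settings.

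| Group A topped up | Result | B 10% | B 25% | B 50% | B 75% |
|---|---|---|---|---|---|
| Never (literal) | t-test significant | 16–19% | 61–71% | 99–100% | 100% |
| | Mann-Whitney significant | 10% | 37–39% | 92–93% | 100% |
| | Expected false difference | 5 µg | 12.5 µg | 25 µg | 37.5 µg |
| Half as often | t-test significant | 7–8% | 16–18% | 40–44% | 73–77% |
| | Mann-Whitney significant | 6% | 12–13% | 37–38% | 70–72% |
| | Expected false difference | 2.5 µg | 6.3 µg | 12.5 µg | 18.8 µg |
| 80% as often | t-test significant | 5–6% | 6–7% | 10–11% | 18–20% |
| | Mann-Whitney significant | 5% | 6% | 9–10% | 15–16% |
| | Expected false difference | 1 µg | 2.5 µg | 5 µg | 7.5 µg |
| Equally often | Either test | about 5% | about 5% | about 5% | about 5% |

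Example of the last line in a block: 50 × 0.50 × (1 − 0.5) = 12.5 µg.

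**4. Sensitivity to the assumed dose** (80 kg, t-test, Group B share 50%). With 25 µg, rejection is 79–90% at ratio 0, 24–30% at 0.5 and 8–9% at 0.8. With 100 µg it is 100%, 50% and 11%.

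**5. Cross-check by formula.** Suppose Group A gets induction fentanyl only (assumed weight SD 10–15 kg) and Group B gets a mean extra 25 µg (assumed SD 20–30 µg). The probability of a significant result is then 96.1% to 99.99%, which agrees with the simulation for the literal reading.

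**The case against.** The strongest reply is that the literal reading is an inference from silence. No sentence forbids fentanyl in Group A. Analgesia is totalled in both groups, and the Introduction speaks of rescue analgesia with the block. The lower planning mean of 106 µg would also need a mean weight near 106 kg if it came from 1 µg/kg alone. Under the discretionary reading no bias is demonstrated: dose, frequency and ratio are all assumed, and the rejection rates run from about 5% to 100%. The false differences reach at most 37.5 µg with a 50 µg top-up, under half the planned 80.5 µg. Recorded haemodynamics, and post-operative pain and morphine under a common rule, might also expose a block that did nothing.

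Much of this stands. The second reading is open, and the table illustrates sensitivity; it does not estimate the bias in this trial. The support for that reading is limited, however. Item 5 is a recording item and gives no dosing rule. Item 3 defines rescue analgesia as post-operative. The group and the source study's dosing behind the 106 µg are not stated. The Protocol's criterion is p < 0.05, which differences well below 80.5 µg can meet, and larger or repeated top-ups would give larger false differences. The secondary outcomes may hint at a problem but cannot repair the primary comparison.

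A further fair point is that a haemodynamic trigger is not neutral between arms. The Protocol lists "Common complications of caudal block in the postoperative period which include hypotension, bradycardia, lower limb numbness and urinary retention", and the block's haemodynamic effect is itself a secondary outcome.

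**Conclusion.** The concern holds. As written, permission for further fentanyl is given to one arm only, on an unquantified cue, and that drug is the primary outcome.

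Under the literal reading the flaw is structural: the expected primary difference is Group B's mean top-up, whether or not the block works. Under the discretionary reading the bias may be negligible if both arms are dosed alike, or large if Group A is topped up much less often for reasons other than analgesia. The documents do not allow its size to be stated. The simulated rates rest on assumed weights, one assumed top-up dose, assumed shares and assumed ratios.

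This should be corrected, because the Protocol does not fix the rule that generates its main result. Confidence in the practical size of the bias is only moderate.

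**What to change.** Delete the fentanyl clause from the Group B paragraph and put one rule in the common Intraoperative setting list, for example:

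*In both groups, after induction, fentanyl [dose] is given when heart rate or mean blood pressure exceeds baseline by [x]% for [y] minutes; each dose, its time and its trigger are recorded.*

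The sponsor's clinicians choose the dose, x and y. Baseline heart rate and mean pressure are already observed. The protocol and the report should also say that the block can itself lower pressure and heart rate, so the trigger is not fully arm-neutral. The rule removes the difference in permission and narrows discretion; it does not replace blinding.

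**Cost.** Wording in two places and one line on the anaesthesia record; no extra patients. There are two downsides:

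- The fentanyl difference may shrink. Power has room for this: 30 per arm detects about 16 µg at 90% power with the planning SDs. With an assumed SD of 40 or 60 µg it detects 0.851 × 40 = 34 µg or 0.851 × 60 = 51 µg, against the planned 80.5 µg.
- Some bias can remain. If the block's haemodynamic effect alone made Group A reach the trigger 80% as often, the 80% rows of the table would still apply, with t-test rejection of up to 18–20% at a Group B share of 75%.
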